Study Protocol

Meaning-centered Intervention (PSY-2324-S-0451)

Procedure

Recruitment will take place through the student-participant pool of the Faculty of Behavioral and Social Sciences at the University of Groningen. Participants for the trial are selected based on an online screening study. After reading the study information and giving consent, participants are screened on i) treatment status (“Are you currently in treatment for a depressive or anxiety disorder?”) ii) suicidality (item 9 of the BDI-II; Beck et al. 1996), and iii) depressive and anxiety symptoms per PHQ-4 (Kroenke et al., 2009; Löwe et al., 2014). Participants who display a total score of ≥ 2 on the PHQ-4, who are not in treatment, and do not indicate suicidality were eligible for the trial.

Upon meeting the eligibility criteria, participants were invited to participate in the meaning-centered intervention trial via an email which explains the most important information of the study (e.g. design, content of the meaning-intervention, compensation) and includes a link to the online environment of the baseline assessment. After reading the study information and giving consent, participants fill in demographics (age, gender, nationality, primary language) and their availability for the first intervention session. After that, they fill in a series of questionnaires that are presented in randomized order:

- Meaning in Life Questionnaire (MLQ; Steger et al., 2006)
- Three-dimensional Meaning Scale (3DM; Martela & Steger, 2023)
- Balanced Measure of Psychological Needs (BMPN; Sheldon & Hiltper, 2012)
- Self-control: Brief Self-control Scale (BSCS; Tangney, Baumeister, & Boone, 2004)
- Intolerance of Uncertainty scale (Carlton et al., 2007)
- A Short Boredom Proneness Scale (Struk et al., 2017)
- Depression, Anxiety and Stress Scales-21 (DASS-21; Lovibond, 1995)
- Short form of social interaction anxiety scale and social phobia scale (SIAS-6, SPS-6; Peters et al., 2012)
- Loneliness Scale (de Jong-Gierveld & van Tilburg, 1999)
- Robert UCLA Loneliness Scale (Goossens et al., 2014)
- Rosenberg self-esteem scale (Rosenberg, 1979)
- Drinking: Alcohol Use Disorders Identification Test (AUDIT; Saunders, Aasland, Babor, de la Fuente, & Grant, 1993)
- “Govern” subscale of the Temptation and Restraint Inventory (Collins & Lapp, 1992)
- Drinking Motive Questionnaire (Cooper, 1994)
- Drinking Pattern Behaviour (Kurihara et al., 2022)

Then, participants are asked if they were familiar with the names of any intervention trainer involved in the study. Finally, they are thanked for their participation and informed about the next steps. After completing the baseline assessment, they are randomly assigned to either the waitlist or the intervention condition by simple randomization using a true random number

generator ([random.org](https://www.random.org)). Participants in the intervention condition are contacted by a trainer that would then conduct the intervention session with them in either Dutch, English, or German. Participants in the intervention condition followed six 1-hour online sessions of a meaning-centered intervention for internalizing symptoms (for details on the original intervention designed for eating disorders, see van Doornik et al., 2024), with sessions taking place approximately every 4 days. Immediately after completion of the last intervention session, participants in the intervention condition will receive the link to the post-assessment questionnaire. Participants in the waitlist condition will be informed that they are assigned to the waitlist condition and that in a month from now they will receive the link to the post-assessment. Waitlist participants will be also informed that they can follow the intervention themselves once data collection completes, prospectively in June 2026. One month after the post-assessment, both conditions will be asked to complete the follow-up assessment. For all assessments, participants will be compensated with SONA credits.

Statistical Analyses

All analyses will be run in R. All analyses will be run as completer analysis, given our aim to assess the efficacy of the present intervention in a subclinical sample (Silverman et al., 2024). Missing values will be imputed using predictive mean matching. Analyses will be run with and without influential observations (i.e., observations showing high standardized residuals and/or leverage). Differences in outcomes between analyses with and without influential points will be reported.

A minimal sample size of $N=128$ is required to yield power of 0.8 based on testing a one-way ANCOVA with α -level of .05, effect size of $f=0.25$, number of groups = 2, max. number of covariates = 2, and numerator $df=1$. We aimed to recruit 142 participants, assuming a drop-out rate of 10%.

Primary Outcomes: Meaning in life and Internalizing Symptoms

H1a: The meaning-centered intervention increases meaning in life at post assessment and follow-up, compared to a waitlist control.

H1b: The meaning-centered intervention reduces internalizing symptoms at post assessment and follow-up, compared to a waitlist control.

The effect of the intervention on both meaning and internalizing symptoms will be tested by running a MANCOVA with post-assessment sum score of presence subscale of the MLQ and DASS-21 sum score as dependent variables, with baseline presence sum score and baseline DASS-21 sum score as covariate and condition (intervention, waitlist) as the between-subjects factor. This step will be repeated with the follow-up scores as dependent variables and baseline and post-assessment score as covariates. All resulting p values will be tested against an alpha level of 0.05.

The effect of the intervention specifically on either primary outcome will be tested using ANCOVAs. The first ANCOVA will test the effect on meaning in life, with post-assessment sum score of presence subscale of the MLQ as dependent variable and baseline presence sum score as

covariate, with condition (intervention, waitlist) as a between-subjects factor. This step will be repeated with the follow-up scores as dependent variable and baseline and post-assessment score as covariates.

The effect of the intervention on internalizing symptoms will be tested by an ANCOVA with post-assessment DASS-21 sum score as dependent variable and baseline DASS-21 sum score as covariate, with condition (intervention, waitlist) as a between-subjects factor. This step will be repeated with the follow-up scores as dependent variable and baseline and post-assessment score as covariates.

Secondary Outcomes: Dyscontrolled Drinking and Three-Dimensional Meaning

H2a: The meaning-centered intervention reduces dyscontrolled drinking at post assessment and follow-up, compared to a waitlist control.

H2a: The meaning-centered intervention increases coherence, purpose, and significance at post assessment and follow-up, compared to a waitlist control.

The effect of the intervention on the secondary outcomes dyscontrolled drinking and three-dimensional meaning will be tested using ANCOVAs. The effect on dyscontrolled drinking will be tested using post-assessment sum score of the Govern subscale of the Temptation and Restraint Inventory as dependent variable and baseline Govern sum score as covariate, with condition (intervention, waitlist) as a between-subjects factor. This step will be repeated with the follow-up scores as dependent variable and baseline and post-assessment score as covariates. The effect on three-dimensional meaning will be tested with three ANCOVAs with post-assessment coherence, purpose, and significance sum score as dependent variable and their baseline scores as covariate, with condition (intervention, waitlist) as a between-subjects factor. This step will be repeated with the follow-up scores as dependent variable and baseline and post-assessment score as covariates. The alpha level for the *p* values resulting from the ANCOVAs for the secondary outcomes will be adjusted by Bonferroni-Holm multiple testing correction.

Secondary Analysis: Invariant Causal Prediction

We will analyze the causal relationships between all assessed variables via the Invariant causal prediction (ICP) algorithm (Meinshausen et al., 2016) using code adapted from Kossakowski et al. (2021). The ICP infers causal relationships by testing the residual distribution of a target variable given all possible subsets of predictors against the residual distribution of that variable in the other condition (i.e., intervention or waitlist), using a Kolmogorov-Smirnov test. This procedure is followed for every variable as target variable. Predictors of the target variable which are part of each invariant subset are implied as causes. A subsampling procedure tests which of those relationships hold across random subsamples of participants. We will run the ICP on the post-change scores of all variables. We will also run the ICP on the follow-up-baseline change scores of all variables. Missing data will be imputed using predictive mean matching imputation in the "mice" package (van Buuren & Groothuis-Oudshoorn, 2011). The ICP corrects for familywise error rates using Bonferroni. The ICP will be used for exploratory analysis and inspected for the hypothesized relationships for primary and secondary outcomes described above as well as for the causal link between meaning and internalizing symptoms through intolerance of uncertainty (Ostafin et al., 2022).

References

- Beck, A. T., Steer, R. A., & Brown, G. K. (1996). Manual for the Beck Depression Inventory-II. San Antonio, TX: Psychological Corporation.
- Carleton, R. N., Norton, M. A., & Asmundson, G. J. (2007). Fearing the unknown: a short version of the Intolerance of Uncertainty Scale. *Journal of Anxiety Disorders*, 21(1), 105–117. <https://doi.org/10.1016/j.janxdis.2006.03.014>
- Collins, R. L., & Lapp, W. M. (1992). The Temptation and Restraint Inventory for measuring drinking restraint. *British Journal of Addiction*, 87(4), 625–633. <https://doi.org/10.1111/j.1360-0443.1992.tb01964.x>
- Cooper, M. L. (1994). Motivations for Alcohol Use Among Adolescents: Development and Validation of a Four-Factor Model. *Psychological Assessment*, 6 (2), 117-128.
- de Jong-Gierveld, J., & van Tilburg, T. G. (1999). *Manual of the Loneliness Scale*. Methoden en technieken. <https://doi.org/10.17605/osf.io/u6gck>

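### In the intervention arm the only stated route to post-assessment is finishing the last session, so early stoppers have no stated outcome assessment, while the waitlist is assessed by calendar

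*Combined protocol and SAP*

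**What the plan says.** The Procedure section sets a different trigger for post-assessment in each arm.

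- Intervention: "Immediately after completion of the last intervention session, participants in the intervention condition will receive the link to the post-assessment questionnaire". There are six sessions.
- Waitlist: participants are told of their assignment and that "in a month from now they will receive the link to the post-assessment".
- Follow-up: "One month after the post-assessment, both conditions will be asked to complete the follow-up assessment".

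No sentence says whether, or when, an intervention participant who stops before the sixth session is sent either link.

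The Statistical Analyses section then states: "All analyses will be run as completer analysis, given our aim to assess the efficacy of the present intervention in a subclinical sample". It does not say whether a completer is someone who finished the sessions or someone who returned the questionnaires. It adds: "Missing values will be imputed using predictive mean matching". On numbers, a minimum of 128 is required and "We aimed to recruit 142 participants, assuming a drop-out rate of 10"%, with no split by arm. The follow-up models for the primary and secondary outcomes take the post-assessment score as a covariate.

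**The concern.** Randomisation makes the arms comparable at baseline. On the text as it stands, being measured afterwards requires finishing six sessions in one arm and nothing comparable in the other. If those who stop differ prognostically from those who finish, beyond what the baseline score captures, the condition effect compares a selected part of one arm with a differently selected other arm. A missing post-assessment also carries forward, because follow-up is dated from it and the follow-up models adjust for it.

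The completer statement does not settle this. It says who is analysed, not who is measured. An analysis set can be reconsidered after data collection, but outcomes never requested cannot be recovered. Without them, neither the team nor a reader can check the completer result against an estimate in everyone randomised.

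The concern is about prognosis. If non-finishers merely benefit less, the completer contrast answers a different question and is not biased for that reason.

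**Working it through.** **The plan's own figures.** For an ANCOVA F test with f = 0.25, alpha 0.05, numerator df 1 and two covariates, the denominator df is 128 − 2 − 2 = 124 and the noncentrality is 0.25² × 128 = 8. Power is 0.801, so 128 is reproduced. For drop-out, 128 / 0.9 = 142.2, which agrees with 142. With two equal groups, f = 0.25 corresponds to d = 2 × 0.25 = 0.5. None of these figures needs correcting.

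**Inputs for the illustration**

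- From the documents: planned loss 142 − 128 = 14.
- Assumed: 1:1 allocation, so 142 / 2 = 71 per arm; post-assessment SD of 1; no true effect.
- Assumed: δ, the amount by which finishers would score better than non-finishers at equal baseline, set at 0.2, 0.5 and 0.8 SD.
- Assumed: r, the baseline-post correlation, set at 0, 0.6 and 0.8.

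**Shift.** If a share p of an arm is unmeasured, the mean of those measured exceeds the mean of the whole arm by p × δ. The contrast therefore shifts by

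(p × δ) in the intervention arm − (p × δ) in the waitlist arm.

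*All 14 losses in the intervention arm.* p = 14/71 = 0.197. The shift is 0.197 × (0.2, 0.5, 0.8) = 0.039, 0.099, 0.158 SD, or 8%, 20% and 32% of d = 0.5.

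*Seven losses in each arm.* p = 7/71 = 0.099 in both. With the same δ in both arms the two terms cancel and the shift is 0. If the waitlist losses are unrelated to prognosis, the shift is 0.099 × (0.2, 0.5, 0.8) = 0.020, 0.049, 0.079 SD.

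*Other cases.* At δ = 0 there is no shift. If people stop because they are already doing better, δ is negative and the shift works against the intervention.

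**False-positive rate with all 14 losses in the intervention arm.** 57 remain against 71. SE = √(1 − r²) × √(1/57 + 1/71), and √(1/57 + 1/71) = 0.178. The two-sided rejection rate comes from a noncentral t with 57 + 71 − 3 = 125 df and noncentrality shift/SE.

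| r | SE | δ = 0.2 | δ = 0.5 | δ = 0.8 |
|---|---|---|---|---|
| 0 | 0.178 | 6% | 9% | 14% |
| 0.6 | 0.142 | 6% | 11% | 20% |
| 0.8 | 0.107 | 7% | 15% | 31% |

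For example, at r = 0.6 and δ = 0.8, 0.158 / 0.142 = 1.11, which gives about 20%.

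**Imputation.** Predictive mean matching fills a gap with an observed value from a donor. If no intervention non-finisher has a post score, every donor is a finisher or a waitlist participant. In a simulation with 71 per arm, r = 0.6 and 14 unmeasured, at δ = 0.5 the shift was 0.100 SD both for completers only and after imputation from baseline and condition. That simulation made stopping depend on the baseline-adjusted outcome, so it shows what happens if stopping works that way, not that it does.

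**The case against.** The strongest reply is that the Procedure section is a short account of the expected course and is silent on people who leave it. A reader might infer that early stoppers are denied the questionnaires. The documents do not say so, and nothing in them shows that stoppers were not contacted. That stands, and the point is confined to what is stated.

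A second reply is that the team chose a completer analysis for an efficacy aim. If 'completer' means session completer, sending links to stoppers changes no planned result. That also stands. What the links provide is the possibility of an all-randomised analysis beside the planned one. The shift would vanish only with both that analysis and full response, and full response is unlikely.

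A third reply is that the size is assumed. A reader might take 20%, or 31%, as this trial's false-positive rate. The documents do not support that: they give no drop-out by arm, no difference between stoppers and finishers, and no baseline-post correlation. The table uses the least favourable split, and balanced losses could leave no shift at all.

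A fourth is that imputation may be meant only for gaps among completers, and could draw on the many other baseline measures. The plan specifies neither. Richer predictors would help only so far as they explain who stops.

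These replies limit the size of the point. They do not supply the missing route to assessment.

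**Conclusion.** The point holds as a gap in stated outcome collection that depends on adherence in one arm only. Combined with an undefined completer analysis, it means that the plan followed as written may compare session finishers with a waitlist arm under no such condition, and later analysis could not recover stoppers who were never measured.

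The magnitude is illustrative: 0.04 to 0.16 SD against a planned 0.5 if all 14 losses fall in the intervention arm and stoppers are 0.2 to 0.8 SD worse at equal baseline. It could be smaller, nil or reversed. An actual bias is not shown. The case for acting rests on the low cost of the change and on unmeasured outcomes being unrecoverable, not on any one of these figures. It is a change that should be made.

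**What to change.** - Keep the link at the last session for those who finish.
- Send the post-assessment link one month after notification of assignment to intervention participants who have stopped sessions and have not withdrawn consent. Anyone still attending at that time gets it after their last session.
- Send the follow-up link one month after the date of the post-assessment link, whether or not that assessment was answered.
- Define 'completer' as session completion, questionnaire completion or both.
- Report an all-randomised analysis with the same models beside the completer analysis, and give by arm the numbers randomised, sent each link and assessed.
- If some assessments have closed, apply this to those still open and report how many intervention participants were never sent a link.

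If stoppers are already being contacted, the protocol should state the rule in use.

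The cost is two or three protocol sentences, one e-mail rule, and SONA credits at two assessments for perhaps 7 to 14 more people. Sessions and finishers' post-assessment timing do not change. The downside is that some non-finishers will not answer, so the all-randomised analysis reduces the selection without removing it. Those who do answer are measured at a month rather than straight after a session.

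### All analyses are restricted to undefined completers, with no as-randomised analysis and no stated assessment route for participants who stop sessions, so one arm could be selected on adherence

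*Combined protocol and SAP*

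**What the plan says.** On the analysis population, the Statistical Analyses section states: "All analyses will be run as completer analysis, given our aim to assess the efficacy of the present intervention in a subclinical sample". A paper on intention-to-treat questions is cited in support. No section says whether a completer is someone who finished the sessions or someone who returned the questionnaires, and no minimum number of sessions is given. No as-randomised analysis appears as a primary, secondary or sensitivity analysis; the only sensitivity analysis concerns influential observations.

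On assessment, the Procedure gives the two arms different triggers. For the intervention arm: "Immediately after completion of the last intervention session, participants in the intervention condition will receive the link to the post-assessment questionnaire". Waitlist participants are told that "in a month from now they will receive the link to the post-assessment". Then: "One month after the post-assessment, both conditions will be asked to complete the follow-up assessment". The Procedure does not say what happens to someone who stops before the sixth session.

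On missing data: "Missing values will be imputed using predictive mean matching". The plan does not say whether this covers people who drop out or only gaps among completers. On numbers: "We aimed to recruit 142 participants, assuming a drop-out rate of 10" per cent.

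**The concern.** H1 and H2 are causal comparisons with the waitlist, and randomisation supports them only if the arms are compared as allocated. If the Procedure is followed to the letter, someone who leaves after session three is never sent a post-assessment. Follow-up is timed from the post-assessment, and the follow-up models use the post-assessment score as a covariate, so that person is lost there too. Every waitlist member is invited, with nothing to complete first. The comparison would then be between people who finished six sessions and everyone on the waitlist who answers a questionnaire.

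An efficacy aim does not remove this problem, because waitlist members who would have finished six sessions cannot be identified. If finishing is related to outcome beyond what baseline explains, part of the measured difference is selection. This touches every confirmatory test, and outcomes that were never collected may not be recoverable.

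**Working it through.** **1. The plan's own figure.** Inputs from Statistical Analyses: f = 0.25 (d = 0.50), α = 0.05, two groups, two covariates. Noncentral F with λ = N × f² and df 1 and N − 4: at N = 128, λ = 8.0 and power is 0.801, so 128 reproduces. 128/0.9 = 142.2 and 142 × 0.9 = 127.8, so the size is planned on those left after drop-out. About 14 losses are expected. If all fell in one arm of 71, that would be 14/71 = 19.7% of the arm.

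**2. Bias in the post-assessment ANCOVA.** Assumptions not in the documents: 71 per arm (the allocation ratio is not stated), no true effect, and drop-outs worse than completers by a gap g in adjusted SD units, the same in both arms. With loss p1 (intervention) and p0 (waitlist):

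- bias = p1 × g − p0 × g
- SE = √(1/n1 + 1/n0), with n1 = 71(1 − p1) and n0 = 71(1 − p0)
- type I error from a two-sided 5% z test

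Example, 15%/5% with g = 1.0: bias = 0.15 − 0.05 = 0.10; n1 = 60.35, n0 = 67.45; SE = 0.177; type I error 8.7%.

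| Loss, intervention/waitlist | g = 0 | g = 0.5 | g = 1.0 |
|---|---|---|---|
| 10%/10% | 0; 5.0% | 0; 5.0% | 0; 5.0% |
| 12%/8% | 0; 5.0% | 0.02 SD; 5.2% | 0.04 SD; 5.6% |
| 15%/5% | 0; 5.0% | 0.05 SD; 5.9% | 0.10 SD; 8.7% |
| 20%/0% | 0; 5.0% | 0.10 SD; 8.7% | 0.20 SD; 20.2% |

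All four rows have 10% overall loss, as planned. Equal loss cancels only if the gap is also equal: 10%/10% with a gap in the intervention arm alone gives 0.05 SD (5.9%) at g = 0.5 and 0.10 SD (8.7%) at g = 1.0. If loss is heavier in the waitlist the sign reverses: 5%/15% with g = 1.0 gives −0.10 SD.

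A different selection model gives the same pattern. With 20% stopping in the intervention arm only, a baseline-outcome correlation of 0.6, and a correlation of 0, 0.3 or 0.5 between adherence and the outcome residual, simulated type I error was 0.05, 0.09 and 0.17.

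**3. Follow-up.** Here the post-assessment score is a covariate and absorbs much of the gap. In the extreme 20%/0%, g = 1.0 case, with the same gap at both times, simulation gives about 0.03 to 0.07 SD for assumed residual correlations of 0.8 and 0.6. A rough hand check, 0.20 × (1 − r), gives 0.04 and 0.08. The exact value depends on how that correlation is defined; the order of size does not. The MANCOVA was not computed.

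**4. Does imputation help?** Simulated bias at post-assessment, g = 1.0, baseline slope 0.6, 10 imputations:

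| Loss | Completers only | Predictive mean matching, no drop-out outcomes | 70% of drop-outs observed, drop-out indicator in model |
|---|---|---|---|
| 15%/5% | 0.105 | 0.104 | 0.006 |
| 20%/0% | 0.202 | 0.201 | 0.007 |

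Imputation without any drop-out outcomes changes nothing. Collecting the outcomes removes most of the bias, provided responding drop-outs represent the others. If non-responding drop-outs are a further 1.0 SD worse, about 0.20 × 0.3 × 1.0 = 0.06 SD remains at 20%/0%.

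**5. Power of an all-randomised analysis.** Assume d = 0.50 in session completers; λ = N × d²/4, df 1 and N − 4.

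| Stopping in intervention arm | Stoppers gain | Diluted d | Power, N = 142 | Power, N = 128 |
|---|---|---|---|---|
| 10% | nothing | 0.50 × 0.9 = 0.45 | 0.76 | 0.71 |
| 20% | nothing | 0.50 × 0.8 = 0.40 | 0.66 | 0.61 |
| 10% | half | 0.475 | 0.80 | 0.76 |
| 20% | half | 0.45 | 0.76 | 0.71 |

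**The case against.** The strongest reply is that one-arm selection is inferred from silence. The Procedure describes the ordinary path through the trial. It never says that people who stop are refused a link, and it says both conditions will be asked to complete follow-up. If *completer* means questionnaire responder and stoppers do receive links, only ordinary non-response remains. This stands: a reader might infer that the plan excludes stoppers from assessment, and the documents do not establish that. They do leave the analysis population open, and the only trigger they state depends on finishing the sessions.

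Second, the completer choice is deliberate and referenced, and which population is primary is partly a choice of estimand. This also stands in part. The documents do not show that a completer analysis is illegitimate, so the all-randomised analysis could be co-reported instead of being the sole primary. But the rationale neither defines a completer nor makes the arms comparable after selection.

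Third, imputation may be meant to cover drop-outs. The plan does not say so. Imputing drop-outs sits awkwardly with a completer analysis, and without their outcomes it would not remove the bias.

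Fourth, the harm is modest at the planned loss rate unless loss is lopsided and the gap large. That is correct.

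**Conclusion.** The concern holds as a defect in the stated rules: completers are undefined, no as-randomised analysis is planned, and post-assessment is triggered by adherence in one arm and by elapsed time in the other. Following the plan as written can select the intervention group on adherence. Whether that will happen, how much bias would follow and in which direction cannot be settled from the documents.

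Three stronger readings are tempting and unsupported. One is that the trial will show a falsely favourable effect: bias is zero if completion is unrelated to outcome given baseline, or if loss and gap are equal in both arms, and it can reverse. Another is that type I error is about 20%: that needs all loss in one arm and a 1.0 SD gap, both assumptions, whereas 15%/5% gives 5.9% to 8.7% for gaps of 0.5 to 1.0 SD. The third is that the same bias carries to every test: the figures apply to the post-assessment ANCOVA, follow-up bias is smaller, and the MANCOVA was not assessed.

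This should be settled before data collection ends.

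**What to change.** 1. **Assessment.** Send post-assessment and follow-up links to every randomised participant, whatever number of sessions was attended. Session completers keep the planned timing. Those who stop get the post-assessment link at a fixed time, for example one month after assignment as for the waitlist, with follow-up timed from the date that link was sent. Contact earlier drop-outs where still possible. Moving everyone to one calendar schedule is a separate choice and not needed here: the plan has six sessions "with sessions taking place approximately every 4 days", so five gaps or about 20 days, and a common schedule would change when session completers are measured.
2. **Analysis.** Pre-specify an analysis of all randomised participants in their allocated arms for H1 and H2, preferably as primary and at least co-reported with equal prominence. Use predictive mean matching as multiple imputation, and state that it covers people who stop. Include an indicator for stopping only if some stoppers' outcomes are observed; otherwise its effect cannot be estimated. Where none are observed, report a sensitivity analysis shifting stoppers' imputed values by 0 to 1.0 SD.
3. **Wording.** Define *completer*, and label the completer analysis as a non-randomised efficacy comparison.

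**Cost.** E-mails and credits ("For all assessments, participants will be compensated with SONA credits") for about 7 to 14 students (71 × 0.10 to 71 × 0.20), plus SAP wording. The larger cost is dilution. If stoppers gain nothing, power is about 0.76 (10% stopping) or 0.66 (20%) with 142 outcomes observed, and about 0.71 or 0.61 if information falls to 128. The stated 0.80 should therefore be described as conditional on the effect in completers. Outcomes already missed may not be recoverable; for those participants only the shift analysis adds information.

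### The follow-up models adjust for the post-assessment score, which the intervention itself is meant to change, so they do not test the hypothesised difference from waitlist at follow-up

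*Combined protocol and SAP*

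**What the plan says.** In the combined protocol and SAP, under Primary Outcomes, H1a reads: "The meaning-centered intervention increases meaning in life at post assessment and follow-up, compared to a waitlist control". H1b makes the same two-time-point claim for internalizing symptoms: "The meaning-centered intervention reduces internalizing symptoms at post assessment and follow-up, compared to a waitlist control". Under Secondary Outcomes, the hypotheses on dyscontrolled drinking and on coherence, purpose and significance take the same form.

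At post-assessment, every model adjusts for baseline scores only. At follow-up the covariates change. For the MANCOVA: "This step will be repeated with the follow-up scores as dependent variables and baseline and post-assessment score as covariates". For the two primary ANCOVAs, the Govern ANCOVA and the three 3DM ANCOVAs: "This step will be repeated with the follow-up scores as dependent variable and baseline and post-assessment score as covariates".

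The Procedure section puts randomisation after the baseline assessment, post-assessment after the last session in the intervention arm (a month on for the waitlist), and follow-up one month after post-assessment. The sample size paragraph assumes "number of groups = 2, max. number of covariates = 2", which fits the follow-up ANCOVAs.

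**The concern.** Baseline is measured before randomisation, so adjusting for it leaves the randomised contrast intact and usually sharpens it. The post-assessment score is measured after randomisation, and the plan first tests it for an intervention effect. Adjusting for it removes from the follow-up contrast the part of the effect already present at post-assessment. What remains is change beyond that predicted by the post score, among people with equal post scores. That is a different question from the one in H1 and H2. The comparison also loses the protection of randomisation, because unmeasured causes shared by the post and follow-up scores can bias it.

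Follow-up is half of each hypothesis. A benefit that lasts could be reported as no effect at follow-up, and a benefit that has faded could be reported as harm.

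**Working it through.** **The plan's own figure.** With f = 0.25, alpha 0.05, numerator df 1 and 2 covariates, the noncentral F with noncentrality f²N gives power 0.8014 at N = 128 and 0.7982 at N = 127. The stated N = 128 reproduces. With 128/0.9 = 142.2, so does the target of 142 (143 if rounded up).

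**What the follow-up model estimates.** Let dP and dF be the condition effects at post and follow-up (positive = benefit), and b the slope of follow-up on post given baseline. The condition coefficient is

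coefficient = dF − b × dP.

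It equals dF only if dP = 0 or b = 0. H1 and H2 predict dP ≠ 0, and repeated scores on one scale a month apart can be expected to correlate positively.

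**Inputs.** From the plan: N = 128, f = 0.25 (d = 0.5 with two equal groups) and alpha 0.05. Assumed: equal arms, a two-sided test, dP = 0.5, and the correlations, which the documents do not give. Two scalings are shown because the plan does not say whether f refers to raw or baseline-adjusted variation.

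**Scaling 1: baseline-adjusted SD = 1.** Here b = rho, the partial correlation of post and follow-up given baseline.

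- Collinearity of condition with post: R² = (dP²/4)/(1 + dP²/4) = 0.0625/1.0625 = 0.0588.
- SE = √[(1 − rho²) × (4/128)/(1 − R²)], with 124 df.
- Example, rho = 0.6, effect maintained: coefficient = 0.5 − 0.6 × 0.5 = 0.20; SE = √(0.64 × 0.03125 × 1.0625) = 0.146; noncentrality = 0.20/0.146 = 1.37; power 28%.

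| rho | Maintained (dF = 0.5): coefficient | Power | Faded (dF = 0): coefficient | Significant against intervention |
|---|---|---|---|---|
| 0.4 | 0.30 | 43% | −0.20 | 22% |
| 0.5 | 0.25 | 35% | −0.25 | 35% |
| 0.6 | 0.20 | 28% | −0.30 | 53% |
| 0.7 | 0.15 | 21% | −0.35 | 76% |
| 0.8 | 0.10 | 15% | −0.40 | 95% |
| Baseline only | 0.50 | 80% | 0.00 | 2.5% |

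Partial fading can vanish altogether. With dF = 0.3 and rho = 0.6 the coefficient is 0.3 − 0.6 × 0.5 = 0, and the rejection rate is 5%, against 39% power with baseline only. To keep a partial f of 0.25, dF would have to grow to 0.5 rho + 0.5√(1 − rho²), which is 0.66 at rho 0.4 and 0.71 at rho 0.7.

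**Scaling 2: raw SD = 1.** Here b = (r_post,FU − r_base,post × r_base,FU)/(1 − r_base,post²). For correlations 0.6/0.5/0.7, b = (0.7 − 0.30)/0.64 = 0.625.

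| r base-post / base-FU / post-FU | b | Maintained: coefficient | Power, plan vs baseline only | Faded: coefficient | Significant against intervention |
|---|---|---|---|---|---|
| 0.5 / 0.5 / 0.5 | 0.333 | 0.33 | 60% vs 90% | −0.17 | 20% |
| 0.6 / 0.6 / 0.6 | 0.375 | 0.31 | 62% vs 94% | −0.19 | 27% |
| 0.7 / 0.7 / 0.7 | 0.412 | 0.29 | 67% vs 98% | −0.21 | 39% |
| 0.6 / 0.5 / 0.7 | 0.625 | 0.19 | 30% vs 90% | −0.31 | 66% |
| 0.7 / 0.6 / 0.8 | 0.745 | 0.13 | 20% vs 94% | −0.37 | 91% |

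**Simulation** (4,000 trials per scenario, equal correlations 0.6) agrees: ANCOVA power 63% vs 94% for a maintained effect, and 27% significant against the intervention after complete fading. For the two-outcome MANCOVA with cross-outcome correlation 0.4, maintained-effect power is 63% vs 97%. After complete fading, 25.5% of planned tests are significant, nearly all against the intervention, versus 5.2% with baseline only.

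**The case against.** The post-adjusted model answers a legitimate question, namely whether the arms diverge further after treatment ends, and the post score removes residual variance. The documents give no correlations, and the size of the distortion depends on them. Equal raw correlations of 0.5 to 0.7 imply partial correlations of only 0.33 to 0.41, so the most extreme rows of the first table sit at the upper end. In the equal-correlation scenarios the plan keeps 60% to 67% power for a maintained effect. A significant result against the intervention becomes likelier than not only with a strong post-to-follow-up link and a benefit lost entirely within a month. The sample size paragraph names no time point, and its arithmetic is correct. The post-assessment tests adjust for baseline only and are sound, and with no effect at either time point the follow-up test keeps its 5% level.

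All of this stands, but it limits the size and reach of the problem without removing it. Nothing in the plan says that the follow-up test is meant to show further change. No follow-up group test without the post score is planned. The invariant causal prediction analysis of follow-up-baseline change is exploratory and is not a test of group difference. The distortion appears exactly when the intervention works at post-assessment, which is what the hypotheses predict.

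**Conclusion.** The plan is wrong as written on this point, and it must be corrected. The follow-up MANCOVA and all follow-up ANCOVAs estimate something other than the hypothesised difference from waitlist at follow-up. This follows from the algebra and from the order of randomisation and assessments; it does not depend on the assumed correlations.

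The size does depend on them. With d = 0.5 at post, 64 per arm and a positive post-to-follow-up slope, power for a fully maintained effect ranges from 15% to 67% across the scenarios, against 80% to 98% for a baseline-only model. After complete fading, the chance of a significant result against the intervention ranges from 20% to 95%, against 2.5%. That reversal needs the follow-up effect to fall below b × dP; above that point the consequence is attenuation and lost power. The stated power of 0.8 does not carry over to follow-up for an effect that is merely maintained.

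**What to change.** In the follow-up MANCOVA, the primary follow-up ANCOVAs and the secondary follow-up ANCOVAs, drop the post-assessment score and adjust for the same baseline score or scores as at post-assessment. A repeated-measures model with condition contrasts at post-assessment and at follow-up would serve equally well. If change after treatment is of interest, keep the post-adjusted model as an exploratory analysis, labelled as further change after post-assessment and not as a test of H1 or H2. Make the change before the follow-up data are analysed by condition.

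The cost is SAP wording only. The follow-up data are already planned, and the Procedure section offers waitlist participants the intervention only after data collection ends, so the randomised contrast at follow-up is available. Less residual variance is removed, but N = 128 still gives power 0.801 for f = 0.25 with one covariate, so the sample size does not change.
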